SA 1 (primary): Eradication rate at one year will be compared between current recruits (i.e. study patients on adjuvant liquid alginate) and historical controls. Patients will be matched by type of therapy, and to the best of our ability, length of Barrett's.

SA2 (secondary): To compare the duration of treatment required to achieve complete endoscopic eradication of BE in patients treated with the combination of PPI and liquid alginate solution vs. those treated with PPI alone.

SA 3 (tertiary): To compare the number of treatment sessions required to achieve endoscopic eradication of BE in patients treated with the combination of PPI and liquid alginate solution vs. those treated with PPI alone.

Study Design

This is a pilot prospective cohort study at a single tertiary care center. Patients with BE and proven dysplasia (high or low grade) or risk of other abnormality presenting to our tertiary care center interested in endoscopic treatment will be asked to participate in the study. Participation will involve taking 10 mL of Gaviscon Advance four times daily along with twice daily PPI during the treatment duration. The control group will be a historical cohort of Barrett's esophagus patients treated in the last 5 years by the same endoscopists using similar approaches—these are patients who were prescribed twice daily PPI therapy alone during treatment.

Eligibility Criteria

Patients who are already scheduled for treatment of their dysplastic Barrett's esophagus or risk of other abnormality who are planning to undergo EMR, or ablation therapy with cryotherapy (spray or balloon) and/or RFA (with or without EMR) will be eligible for enrollment.

Inclusion criteria (all must be present):

- (1) Age ≥ 18
- (2) Patients already previously scheduled for treatment of complicated Barrett's esophagus
- (3) Long Segment Barrett's ($>3\text{cm}$)

Exclusion criteria:

- (1) Moderate to severe renal impairment, as defined by eGFR < 60 for 2 consecutive readings
- (2) Lack of capacity for decision-making
- (3) Allergy to hydroxybenzoates

- (4) Patients with uncontrolled hypertension or decompensated heart failure
- (5) Pregnancy- patients of child-bearing potential will be tested.
- (6) Patients with elevated calcium or potassium on screening laboratory testing (labs completed within the last month)

Enrollment

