Eligible patients who provide informed consent will be included in this prospective study and asked to take the alginate solution in addition to their twice daily PPI therapy. If patients are on concurrent H2 blocker therapy, this will be stopped after enrollment in the study. Subjects will be primarily recruited in the office setting, following decision to undergo ablation therapy. Upon the start of ablation therapy, patients will start taking 10ml of Gaviscon Advance 30 minutes after every meal and at bedtime (4 daily doses, after breakfast, lunch, dinner and before bed). This will begin on the day of the first endoscopy, after the ablation treatment. PPI therapy will continue as previously prescribed.

Endoscopic treatment

Standard guidelines will be followed for patients undergoing EMR, RFA or cryotherapy or RFA, up to 8-10 cm can be treated during one session and sessions are scheduled every 10-12 weeks. For cryotherapy, approximately the same area can be treated (8-10cm) during one session, and sessions are scheduled every 8-10 weeks. When initial EMR is performed, follow-up endoscopic ablative therapy will be scheduled approximately 8 weeks later. The decision of which therapy to implement depends largely on anatomy and patient preference and will be determined by the endoscopists involved in the study—[name] (PI), [name], or [name]. Furthermore, all decisions pertaining to the need for repeat procedures to address inadequate treatment or incomplete tissue sampling, or the decision to refer for the alternate procedure, will be dictated by the above endoscopists. As mentioned previously, number of sessions to achieve complete eradication of Barrett's varies by length, but on average can take anywhere from 3-5 sessions, depending on initial length of BE as well as existence and size of hiatal hernia³¹.

Follow-up Assessments

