All enrolled subjects will be followed until resolution of Barrett's is achieved, as confirmed by biopsy and endoscopic visualization. A measurement system referred to as the Prague classification³² will be used to document areas of the esophagus with Barrett's and to assess improvement from one endoscopy to another. This system allows the endoscopist to record the area of Barrett's involved by describing the area involved that is circumferential in nature and the area that is patchy. Decrease in surface area involved will help guide the aim for the study. During treatment sessions, pertinent clinical and endoscopic data will be collected (see Appendix A). Immediately prior to each treatment visit, an office visit will take place at the MUSC Gastroenterology endoscopy/outpatient clinic with study personnel including the PI, research coordinator, and/or fellow/resident participating in the study, which will serve to collect data regarding blood pressure, surveillance serum chemistries, treatment experience, adverse events to the drug, or any other issues (see Appendix B). Adherence to the medication regimen will be done by asking patients to bring in all used and unused bottles. IDS will assist in calculating how much drug has been taken and this data will be recorded at each visit. These data will then be entered into a coded RedCap database. At approximately six week intervals, the study research coordinator will call to verify medication regimen adherence as well as any adverse events associated with the study drug.

From the time of biopsy proven remission, patient medical records will be reviewed for up to 2 years to evaluate recurrences rates.

Outcomes

Eradication rate of intestinal metaplasia (complete remission of intestinal metaplasia – CRIM) at one year will be the primary outcome. The length of time to eradication and the number of endoscopic procedures required for CRIM will be the secondary and tertiary outcomes. CRIM will be defined as visual endoscopic evidence of neo-squamous epithelium occupying previous area of Barrett's epithelium combined with biopsies showing normal squamous esophageal epithelium without intestinal metaplasia.

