We will compare the time to complete BE eradication/resolution (CRIM) between the prospective and historical cohorts using Kaplan-Meier time-to-event (time-to-CR) curves. The historical data maintained by the PI have n= 32 patients treated under similar conditions (e.g. facility, physicians) as the study patients who will be prospectively treated. As the purpose of this pilot study is to estimate the time to CRIM with the addition of liquid alginate for approximately 20 enrolled patients, no hypothesis testing will be performed to compare the distributions (hence, no power calculation). Comparisons will be descriptive only. Time-to-CR is assumed to be exponentially distributed and we will use the maximum likelihood estimate to estimate the rate parameter for each cohort. Patients who do not reach CR by the end of the study will be censored at that time. The difference in the rate parameter between cohorts will be calculated with a 95% confidence interval. Median time to CR will be estimated based on these parameters. Median time to CR under current treatments is about 22 months²⁷. If median time to CR with liquid alginate solution is sufficiently improved (e.g. to < 18 months), we will have high-quality pilot data with which to estimate a sample size for a more definitive randomized trial. Additionally, we will tabulate the number of treatments required to achieve CR and compare descriptively between cohorts as a secondary endpoint. Analyses above will also be stratified according to important covariates, such as disease grade and type of treatment (RFA or Cryotherapy).

Data Collection, Management, and Quality Control Procedures

Data entry will occur through RedCap, which will allow for study data to be directly entered into the database by the site via a secure internet connection. In addition to use of passwords and other security measures, all documents containing identifying information on individuals or physicians are considered confidential materials and will be safeguarded to the greatest possible extent. No information identifying a specific person, hospital, or physician will be released to or discussed with anyone other than study staff members. Appendix C shows the data points that will be collected from both the clinical and endoscopic visits.

Study Sites and Timeline

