This is a single center study which will be conducted solely at MUSC. Patients will be monitored with a telephone call every six weeks as mentioned above and they will be provided with information to get in touch with the study team if they have problems between their visits.. Enrollment will be ongoing until an adequate number of subjects have been recruited. Thus, we anticipate that the study can be completed within 2 years.

Monitoring

All study data will be monitored routinely for completeness, timeliness, and consistency by the project manager. Data accuracy will be verified on a quarterly basis by the project manager and principal investigator. Due to a relatively small “n”, all subjects’ data will be reviewed. Discovered discrepancies between recorded study data and information found in medical records will be addressed through discussions between the PI and research coordinator. Subjects may be withdrawn from the study if they are lost to follow up, or if they endorse lack of compliance with liquid alginate solution and/or PPI therapy.

Safety

Gaviscon Advance is considered a very safe medication with a very mild side effect profile. It is widely available in the UK but not available in the US. An FDA IND application has been filed for its use for this study. Gaviscon Advance will be purchased directly from the pharmaceutical company, Reckitt Benckiser. Each 10 mL oral suspension contains 1g sodium alginate and 200 mg potassium hydrogen carbonate (active ingredients). The formulation also contains calcium carbonate, carbomer, sodium saccharin, sodium hydroxide, and so any patients who have been advised to restrict their diet from any of these substances should consult a doctor before taking Gaviscon Advance. Patients who suffer for have suffered from significant kidney or heart disease should speak with a physician before taking Gaviscon. Finally, the formulation includes methyl and propyl para-hydroxybenzoates which may cause allergic reactions (less than 1 in 10,000 patients), including skin rash, itching, difficulty breathing, dizziness, or swelling. Overdosing of the medication may cause bloating. Please see summary of product characteristics – Appendix D).

Any adverse event, either related to Gaviscon Advance or not, will be recorded in pre-treatment clinic and/or treatment visits, and will be evaluated by a safety review committee (see below).

Safety Review Committee

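### Censoring patients without CR at the end of the study counts time after the last endoscopy, when CRIM cannot be seen, and can bias the between-cohort rate difference towards alginate

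*Combined protocol and SAP*

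**What the plan says.** The section Sample Size Calculation and Statistical Consideration compares time to CRIM between cohorts by Kaplan-Meier curves and an exponential model. It fits one maximum likelihood rate per cohort, gives the rate difference with a 95% interval, and derives medians from the rates. The same paragraph gives the one censoring rule: "Patients who do not reach CR by the end of the study will be censored at that time". There is no separate rule for the historical controls. There is also none for patients withdrawn or lost to follow-up, although the Monitoring section foresees both.

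The event needs a procedure. Under Outcomes, "CRIM will be defined as visual endoscopic evidence of neo-squamous epithelium occupying previous area of Barrett's epithelium combined with biopsies" that are free of intestinal metaplasia. Under Endoscopic treatment, for RFA "sessions are scheduled every 10-12 weeks"; for cryotherapy the interval is 8 to 10 weeks.

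The cohorts occupy different calendar windows. Under Study Design, "The control group will be a historical cohort of Barrett's esophagus patients treated in the last 5 years by the same endoscopists"; the statistical section adds "The historical data maintained by the PI have n= 32 patients". The prospective cohort is "approximately 20 enrolled patients", and under Study Sites and Timeline "we anticipate that the study can be completed within 2 years". Follow-up Assessments states: "All enrolled subjects will be followed until resolution of Barrett's is achieved, as confirmed by biopsy and endoscopic visualization". No matching statement covers the controls.

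**The concern.** A patient can contribute a CRIM event only while endoscopies continue. The exponential rate is events divided by person-time, so months after the last endoscopy enlarge the denominator and can add nothing to the numerator. In the Kaplan-Meier curve, the same patients stay in the risk set after anyone has stopped looking.

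The error need not be equal in the two cohorts. If the controls' clock runs to the end of the prospective study, a control can be counted for up to about 5 + 2 = 7 years from the start of treatment. An alginate patient would be counted for about 2 years if the study keeps to its expected length. The cohort with the longer window can absorb more empty time, so PPI alone could look slower than it was. The rate difference and medians are what the pilot would hand to the designers of a randomized trial.

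**Working it through.** The documents derive no event count or sample size, so there is no plan figure to reproduce. The check uses the plan's own estimator: rate = events / person-time, and median = ln 2 / rate.

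**Inputs from the documents.** 32 controls; about 20 alginate patients; control window 5 years; study length 2 years; median under current treatment 22 months.

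**Step 1: closed form for the controls.** Let k of the 32 controls lack CR, and let each carry A months after the last endoscopy. If the correctly censored median is 22 months, correct person-time is (32 − k) × 22 / ln 2. Adding k × A gives

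estimated median = 22 + ln 2 × k × A / (32 − k).

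| k | A = 12 | A = 24 | A = 36 | A = 48 |
|---|---|---|---|---|
| 4 | 23.2 | 24.4 | 25.6 | 26.8 |
| 8 | 24.8 | 27.5 | 30.3 | 33.1 |
| 12 | 27.0 | 32.0 | 37.0 | 42.0 |

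For example, k = 8 and A = 24 give 22 + 0.693 × 8 × 24 / 24 = 27.5 months. Neither k nor A is in the documents.

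**Step 2: both cohorts, no true difference.** Simulation of 4,000 runs with a true median of 22 months in each cohort. Assumptions:
- controls start uniformly over the 5 years before the study;
- alginate patients enter over the first 12 months;
- the study ends at month 24, and the controls' clock runs to that date;
- CRIM is dated at the next endoscopy, every 2.3 months (about 10 weeks);
- endoscopy stops at a constant annual rate, unrelated to response.

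Estimated medians in months:

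| Stopping per year | Control, last endoscopy | Control, study end | Alginate, last endoscopy | Alginate, study end | Control minus alginate, study end |
|---|---|---|---|---|---|
| 0% | 22.6 | 22.8 | 23.2 | 24.4 | −1.6 |
| 5% | 22.6 | 26.6 | 22.7 | 25.0 | 1.6 |
| 10% | 22.6 | 30.8 | 22.8 | 26.3 | 4.5 |
| 20% | 22.7 | 40.7 | 23.0 | 29.5 | 11.2 |
| 30% | 22.7 | 52.6 | 22.9 | 32.9 | 19.7 |

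The 10% row can be checked by hand. Controls average 21.1 events, so 10.9 lack CR, each with 22.8 added months: 0.693 × 10.9 × 22.8 / 21.1 = 8.2, and 22.6 + 8.2 = 30.8. Alginate patients average 7.6 events, so 12.4 lack CR, each with 3.1 added months: 0.693 × 12.4 × 3.1 / 7.6 = 3.5, and 22.8 + 3.5 = 26.3.

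With no early stopping, the added time is 1.2 months per patient without CR, half a visit interval. It then moves the alginate median more, because a larger share of that cohort lacks CR.

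**Step 3: dependence on what the end of the study means for a control.** Take a different set of assumptions: mean 11 months to CR in achievers, controls without CR last examined at 14 months, and alginate patients without CR averaging 18 months to study end.
- Alginate: 4 of 20 without CR gives 0.693 × (16 × 11 + 4 × 18) / 16 = 10.7 months; 6 of 20 gives 0.693 × (14 × 11 + 6 × 18) / 14 = 13.0.
- Controls run to the end of the prospective study (mean 54 months): 6 of 32 without CR gives 0.693 × (26 × 11 + 6 × 54) / 26 = 16.3; 10 of 32 gives 0.693 × (22 × 11 + 10 × 54) / 22 = 24.6. The gaps are 5.6 and 11.6 months.
- Controls run only to the start of the prospective study (mean 30 months): 12.4 and 17.1. The gaps are 1.7 and 4.1 months.
- Controls censored at last endoscopy: 9.9 and 12.0.

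**The case against.** The controls are an existing data set, not enrolled patients, and the plan nowhere says that their clock runs to the end of the prospective study. The rule could be read as the end of each control's own follow-up. That reading is possible, but it is not written. Even on that reading the date is not tied to the last endoscopy, and withdrawn or lost alginate patients are still carried to the study's end.

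A reader might infer that the rule adds years of empty time to the controls and creates a spurious gain of 6 to 12 months. The documents do not support that. The figure needs early stopping by every control without CR and a clock that runs to the end of the prospective study. It also implies correctly censored control medians of 9.9 to 12.0 months, far from the 22 months the plan cites. The same endoscopists treated both groups by similar approaches, and the plan describes repeat procedures where treatment is inadequate. If nobody stopped early, the control median moves by 0.2 months.

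A reader might also measure the bias against the change from 22 to 18 months. In the plan, however, 18 months is a benchmark for the alginate median beside a published 22, not for the difference from these controls. On that benchmark the rule works against alginate. This objection stands.

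Finally, the primary outcome is eradication at one year, and a proportion of all patients does not use the censoring rule. The time-to-CR comparison is descriptive, in a pilot. That limits the consequence but does not make the rate right: a rate difference with an interval is still specified.

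**Conclusion.** The point holds in a limited form. The censoring sentence, followed as written, gives a wrong rate for any patient whose endoscopies ended before the study did, and it leaves the censoring date of the comparator undefined. Because controls have the longer window, the between-cohort rate difference and curves can be biased towards alginate. The alginate median is lengthened at the same time.

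The size cannot be read from the documents. Under the Step 2 assumptions, the spurious difference in medians runs from 1.6 months against alginate with no early stopping, to 4.5 months in its favour at 10% per year and 11.2 at 20%. It shrinks if the controls' time ends sooner, as Step 3 shows. An all-patient one-year proportion is untouched; a 12-month Kaplan-Meier estimate would be affected if endoscopies stopped before then. The sentence should be corrected before the analysis, but nothing in the documents shows that it must decide the result.

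**What to change.** Replace the sentence with: *Patients in either cohort who have not reached CR, including those withdrawn or lost to follow-up, are censored at the date of their last endoscopy that assessed Barrett's epithelium.* Set a data cut-off date for the controls. Report, by cohort, follow-up to last endoscopy and the number without CR.

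In the simulation this gives 22.6 to 22.7 months for controls and 22.7 to 23.2 for alginate at every stopping rate from 0% to 30% per year. The small excess over 22 comes mainly from dating CRIM at the next endoscopy; an interval-censored exponential fit would address that if wanted.

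The cost is a sentence of text, slightly wider intervals, and retrieval of last endoscopy dates for the controls, which the documents do not confirm are held. There is also a statistical cost. If endoscopy stopped because treatment failed, censoring at that point is informative and overstates the rate; the simulation assumed it was not. So report the reasons for stopping where recorded, and show the one-year eradication proportion with all patients in the denominator alongside.

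### The 18-month mark is applied to a point estimate from about 20 patients, which cannot support sizing a randomised trial: with no effect, 21% to 30% of such pilots would still fall below it

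*Combined protocol and SAP*

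**What the plan says.** All of the relevant text is in the section Sample Size Calculation and Statistical Consideration. The aim there is to "estimate the time to CRIM with the addition of liquid alginate for approximately 20 enrolled patients", and "no hypothesis testing will be performed to compare the distributions (hence, no power calculation". The estimator is parametric: "Time-to-CR is assumed to be exponentially distributed and we will use the maximum likelihood estimate to estimate the rate parameter for each cohort". The median follows from it: "Median time to CR will be estimated based on these parameters". A 95% confidence interval is planned for the difference in rates between cohorts. None is planned for the median.

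The benchmark comes next: "Median time to CR under current treatments is about 22 months". Then: "If median time to CR with liquid alginate solution is sufficiently improved (e.g. to < 18 months), we will have high-quality pilot data", continuing "with which to estimate a sample size for a more definitive randomized trial".

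The documents give two readings of follow-up. Follow-up Assessments follows every patient to resolution. The statistical section censors patients without a response when the study ends, and Study Sites and Timeline expects completion within 2 years. No accrual pattern is given.

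**The concern.** The sentence makes the pilot's worth for sizing depend on a favourable point estimate. Two problems follow. First, with about 20 patients the estimated median is imprecise, so it can fall below 18 months when alginate does nothing and miss 18 months when the hoped-for benefit is real. The planned interval on the rate difference does not help, because the condition does not refer to it. Second, an estimate that is carried forward only because it passed a cut is biased toward benefit. A randomised trial sized on it would be too small for the improvement that the plan itself uses as its illustration.

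**Working it through.** The plan states no power, event count or derived sample size, so there is no figure of its own to reproduce. The check asks how the stated condition behaves under the plan's own model.

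**Inputs from the documents:** 20 patients; exponential time to response; maximum likelihood; median 22 months under current treatment; example mark 18 months; study length 24 months.

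**Assumed:** uniform accrual over 0 to 24 months; no withdrawals; for the later trial, 1:1 allocation, two-sided 5% and 80% power.

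**Estimator.** With d events in total follow-up T, rate = d/T and median = ln 2 × T/d.

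**Expected events, true median 22, 24-month study.** With 24 months of follow-up for everyone: 20 × (1 − 2^(−24/22)) = 10.6. With accrual over the full 24 months, λ = ln 2/22 = 0.0315 and 24λ = 0.756, so 20 × [1 − (1 − 0.4695)/0.756] = 6.0.

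**Chance of an estimate below 18.** If all 20 patients are followed to CRIM the result is exact: P(χ² on 40 df < 40 × 18/22 = 32.7) = 21.4%. Under censoring it was simulated, with 200,000 pilots per scenario.

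| Follow-up | Expected events (true 22) | Below 18 if true median 22 | Below 18 if true median 18 | Centre (median) of passing estimates, true 18 |
|---|---|---|---|---|
| All to CRIM | 20 | 21.4% | 53.0% | 15.3 months |
| 24 months each | 10.6 | 25.2% | 50.5% | 14.9 |
| Accrual 6 of 24 months | 9.7 | 26.0% | 50.2% | 14.7 |
| Accrual 12 of 24 | 8.6 | 26.8% | 50.1% | 14.6 |
| Accrual 18 of 24 | 7.4 | 28.2% | 49.6% | 14.4 |
| Accrual 24 of 24 | 6.0 | 30.1% | 49.6% | 14.1 |

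When the true median is 22, the passing estimates centre between 16.1 months (all followed to CRIM) and 14.9 months (accrual over 24 months). Relative to 22 months that is an apparent rate ratio of about 1.37 to 1.48, when the true ratio is 1.00.

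**Interval around an estimate of exactly 18 months.** The limits are 18 × 2d/χ²(0.975, 2d df) and 18 × 2d/χ²(0.025, 2d df), exact for a fixed number of events.
- d = 20: 720/59.34 = 12.1 to 720/24.43 = 29.5 months.
- d = 10: 360/34.17 = 10.5 to 360/9.59 = 37.5 months.

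The no-effect value of 22 lies inside both.

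**Consequence for sizing, with one truth throughout (true median 18).** Events = 4 × (1.96 + 0.8416)² / (ln ratio)² = 31.4/(ln ratio)².
- True effect: ratio 22/18 = 1.222, ln = 0.2007, giving 780 events.
- Sized on the centre of passing estimates with 12-month accrual: 22/14.6 = 1.507, ln = 0.410, giving 187 events.
- Power of 187 events for the true ratio: Φ(0.2007 × √187/2 − 1.96) = Φ(1.372 − 1.96) = Φ(−0.588) = 28%.
- With all patients followed to CRIM, the centre is 15.3 months, which gives 239 events and 34% power.

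**The case against.** The best defence is that this is a pilot and says so. Comparisons are descriptive, 18 months is only an example, and Potential Problems and Pitfalls calls the study hypothesis-generating, concedes the small sample and makes the next step depend on whether the pilot proves informative. An interval on the rate difference is already planned.

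Much of this stands, and it rules out several stronger readings that a reader might infer:

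- *That 18 months is a formal go rule or success criterion.* The text gives an example and attaches no decision to it.
- *That sizing a trial is the pilot's only purpose.* The stated purpose is to estimate time to CRIM, and under Outcomes the primary outcome is eradication at one year.
- *That the missing power calculation is a fault.* It is not, in a descriptive pilot.
- *That a rate difference cannot serve for sizing.* Under an exponential model it can. A ratio is the commoner choice, not the only valid one.
- *That the events implied by passing estimates under no effect can be set against the 780 needed for 22 to 18 months.* That mixes two truths. The working above therefore takes 18 months as true on both sides.
- *That an interval for the ratio to the historical cohort can be computed now.* The documents say "The historical data maintained by the PI have n= 32 patients treated under similar conditions" but give no event count.

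The defence does not rescue the sentence itself. A cut left as an example gives no more protection than a fixed one. The planned interval is not tied to the condition. The small-sample caveat also sits badly with calling the data high-quality because the estimate was favourable.

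**Conclusion.** The concern holds in limited form. The plan attributes to a favourable point estimate a property that a cohort of about 20 does not have. The condition separates no effect from the illustrated effect only weakly: 21% to 30% of pilots pass in the first case and about half in the second. Passing estimates overstate benefit. Sizing on a typical one would give a trial with roughly 28% to 34% power for a true change from 22 to 18 months, across 12-month accrual in a 24-month study and full follow-up.

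These figures rest on exponential times, 22 months as the no-effect median, 20 evaluable patients, and an accrual pattern that the documents do not state. The conclusion does not depend on that pattern: full follow-up is the most favourable case examined and still gives 21%, and slower accrual makes it worse. Unreplaced withdrawals would also raise the no-effect figure. This is a point the sponsor should address, and it does not put the conduct of the pilot in question.

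**What to change.** In Sample Size Calculation and Statistical Consideration:

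1. Report the alginate median and the alginate-to-control rate ratio with 95% confidence intervals (exact or on the log scale), alongside the rate difference already planned.
2. Replace the sentence on the 18-month mark with a statement to this effect: the randomised trial will be sized on a worthwhile difference that the investigators choose in advance; the pilot will supply the rates with their intervals, and accrual, adherence and withdrawal; and an estimated median below 18 months will not by itself be read as evidence of improvement. The plan's own illustration, 22 to 18 months (ratio 1.22), is available as a starting point, but the plan does not call it the smallest worthwhile difference, so the investigators must make that choice.

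The cost is wording and a small amount of analysis, with no added patients, visits or procedures. The downside is that the pilot no longer offers an observed effect on which to size the next trial.

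### No segment-length criterion is stated for the historical controls and SA 1's best-effort length matching does not reach the statistical section, so a length imbalance could bias the descriptive comparison in either direction

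*Combined protocol and SAP*

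**What the plan says.** Eligibility Criteria requires "Long Segment Barrett's" (>3 cm) of enrolled patients. Study Design defines the controls as Barrett's "patients treated in the last 5 years by the same endoscopists using similar approaches" who were prescribed twice-daily PPI alone. It gives them no length limit.

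SA 1, the primary aim, addresses length: "Patients will be matched by type of therapy, and to the best of our ability", where the best-effort factor is the extent of the segment. It gives no ratio, caliper or procedure, and it is attached to the one-year eradication rate. Outcomes confirms that CRIM "at one year will be the primary outcome".

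Sample Size Calculation and Statistical Consideration sets about 20 enrolled patients beside historical data on 32. It plans Kaplan-Meier curves, an exponential rate per cohort, the rate difference with a 95% confidence interval, and a tabulation of treatment counts, all descriptive. Matching is not mentioned. On covariates it says: "Analyses above will also be stratified according to important covariates, such as disease grade and type of treatment (RFA or Cryotherapy".

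Endoscopic treatment says that the session count "varies by length, but on average can take anywhere from 3-5 sessions". The same sentence names the starting segment length, and any hernia, as what this turns on. Under Follow-up Assessments, the Prague classification "will be used to document areas of the esophagus" affected, so enrolled patients will have a length measurement.

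**The concern.** The cohorts are not randomised, so any prognostic factor distributed differently between them enters the contrast. The protocol treats length as prognostic for the number of sessions, and sessions are spaced weeks apart, so an effect on time to CRIM is plausible. Yet length is an entry criterion for one cohort only, a best-effort matching factor in one aim, and absent from the analysis text.

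At stake are the one-year CRIM comparison and the between-cohort rate difference. The planned confidence interval covers sampling error only and would not reveal a length imbalance. The study is meant to inform a larger trial, so a distorted contrast could be carried forward.

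**Working it through.** **Inputs from the plan.** Median time to complete response is about 22 months under current treatment, and below 18 months is the example of sufficient improvement. Cohort sizes are about 20 and 32, the model is exponential, and completion is expected within 2 years. The plan has no power calculation to reproduce.

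**Assumptions (not in the documents).** All patients are followed for 24 months. A quarter of controls differ in length from the enrolled patients and clear at *m* times the rate of the rest. The value 5/3 is the ratio of the ends of the 3-5 session range. It is not a bound.

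**Without imbalance.** Rates are ln2/22 = 0.03151 and ln2/18 = 0.03851 per month. The difference is 0.00700 and the ratio 1.22. One-year CRIM is 1 − exp(−12 × 0.03151) = 31.5% and 1 − exp(−12 × 0.03851) = 37.0%, a difference of 5.5 points.

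**With imbalance.** Write λ = 0.03151.
- Events per control: d = 0.75(1 − e^(−24λ)) + 0.25(1 − e^(−24mλ)).
- Person-months per control: P = 0.75(1 − e^(−24λ))/λ + 0.25(1 − e^(−24mλ))/(mλ).
- Fitted control rate: d/P.
- One-year control CRIM: 1 − [0.75e^(−12λ) + 0.25e^(−12mλ)].

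| *m* | d | P | Control rate | Shift | Apparent ratio | Control one-year CRIM | Difference (points) |
|---|---|---|---|---|---|---|---|
| 1 (balanced) | 0.5305 | 16.84 | 0.03151 | 0 | 1.22 | 31.5% | 5.5 |
| 1.25 (shorter) | 0.5508 | 16.51 | 0.03336 | +0.00185 | 1.15 | 33.0% | 4.0 |
| 5/3 (shorter) | 0.5770 | 16.04 | 0.03597 | +0.00447 | 1.07 | 35.3% | 1.7 |
| 1/1.25 = 0.8 (longer) | 0.5114 | 17.13 | 0.02985 | −0.00166 | 1.29 | 30.1% | 6.9 |
| 3/5 = 0.6 (longer) | 0.4891 | 17.45 | 0.02802 | −0.00348 | 1.37 | 28.7% | 8.3 |

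With 10% shorter controls instead of 25%, the ratio is 1.19 to 1.16 and the one-year difference 4.9 to 4.0 points. With no length difference there is no bias from this source. Stronger assumptions do more: 25% clearing twice as fast gives a ratio of 1.02, and 50% clearing 1.5 times as fast gives 0.99.

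**Against sampling error.** Expected events are 20(1 − e^(−24 × 0.03851)) = 12.1 and 32 × 0.5305 = 17.0. SE = √(0.03851²/12.1 + 0.03151²/17.0) = 0.01347, so the 95% half-width is 1.96 × 0.01347 = 0.0264 and the interval is −0.019 to 0.033 per month.
- Shorter controls: 0.00185 and 0.00447 are 26% and 64% of the assumed difference of 0.00700, but 7% and 17% of 0.0264.
- Longer controls: 0.00166 and 0.00348 are 6% and 13% of 0.0264.
- One-year CRIM: the half-width is 1.96 × √(0.370 × 0.630/20 + 0.315 × 0.685/32) = 26.6 points, against a bias of 1.5 to 3.8 points with shorter controls.

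**Does restriction alone help?** Dropping the short quarter leaves 24 controls with 24 × 0.5305 = 12.7 events. SE is then √(0.03851²/12.1 + 0.03151²/12.7) = 0.0142 with no bias. Keeping all 32 gives a root-mean-square error of √(0.01364² + 0.00185²) = 0.0138 at *m* = 1.25 and √(0.01389² + 0.00447²) = 0.0146 at *m* = 5/3. Restriction is slightly worse in the first case and slightly better in the second.

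**The case against.** The strongest reply is that this is one combined document and SA 1 already provides for length. The statistical section need not repeat it, and its covariate list is introduced by words that leave it open. This stands in part: nothing in that section contradicts SA 1 or rules length out. But an open list commits to nothing and lets covariates be chosen after outcomes are seen. SA 1's matching is also tied to the one-year rate, so time to CRIM and treatment counts have no stated length control.

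Second, the 32 may already be a selected group. The protocol reports several treatment-naive dysplastic or IMC patients a month. Even an assumed 2 a month over 60 months is about 120. This is fair, but the basis of any selection is not stated and need not be length. The appendices that list the data items are not in the text reviewed, so nothing is inferred about whether length is recorded.

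Third, the bias is small beside the interval, there is no test, and the protocol already concedes limited validity. This stands and limits the weight of the point. It does not remove it, because descriptive comparisons can be confounded too.

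A reader might infer more than the documents support:
- That the controls include short segments, so the comparison is biased against alginate. Control lengths are not given, and longer control segments would act the other way.
- That the signal of a median below 18 months is compromised. That criterion uses the alginate cohort's own median against a literature figure of 22 months, so choosing other controls does not change it.

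**Conclusion.** The gap in the text is real: there is a length criterion for one cohort only, best-effort matching without a method, and an analysis section with neither matching nor a length term. As written, the plan can yield a length-confounded rate difference and one-year comparison, in either direction. That this happens is possible, not shown.

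Under the main assumptions (a quarter of controls shorter, clearing 1.25 to 5/3 times as fast, 24-month follow-up), much of an assumed 22-versus-18-month effect would be hidden in the point estimate, yet sampling error would be far larger. The share and the speed-up are assumptions, and the protocol links length to sessions rather than directly to time. The point should be fixed because the remedy is cheap and carries out what SA 1 intends. It is not grounds for rejecting the pilot.

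**What to change.** Before outcomes are compared:

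1. Apply the >3 cm criterion to the historical controls, or state that the 32 already meet it, and report the resulting number.
2. Tabulate baseline length by cohort, with the number missing.
3. Add to the statistical section one descriptive length-adjusted estimate, from an exponential model with cohort and baseline length, beside the unadjusted results. State how it relates to SA 1's matching. Keep the planned stratified results.

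**Cost.** Chart review for control length, which SA 1 already presumes can be found, plus one regression. If the 32 all qualify, one sentence settles most of the point.

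**Downside.** There may be fewer controls and a wider interval. With an assumed 20 controls and 24-month follow-up, control events fall to 20 × 0.5305 = 10.6 and the half-width rises from 0.026 to 0.029 per month. Restriction alone brings little or no gain in root-mean-square error. Adjustment costs little if length is balanced: in simulations with length unrelated to cohort and outcome, the standard error of the log rate ratio rose by about 1-2% (0.379 to 0.384 with 32 controls followed 24 months). That is a best case, and the loss is larger if length is unbalanced. With about 29 events in all (12.1 + 17.0), the adjusted result stays descriptive.
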